3 STUDY DESIGN

3.1 General Overview of the Study Design

This is a single center, non-randomized, prospective cohort study to comparatively evaluate the implementation of the MvIGS spine navigation system to conventional 2D fluoroscopy for pedicle screw fixation for the treatment of spinal stenosis with degenerative spondylolisthesis of the lumbar spine.

3.2 Duration of the Study

The patients will be clinically followed throughout the course of their hospital admission. The data collected during surgery and postoperative course will be used to evaluate the efficacy of the MvIGS spine navigation system.

As designed, a total of 130 patients are to be enrolled in the study, with 65 patients per treatment group. Based on this sample size, rate of patient accrual, and the prescribed follow-up time, the total duration of the study is projected to be approximately 9 months.

3.3 Outcome Measures Recorded During the Study

Time point measurements in surgery, including total operative length, will be recorded on the day of surgery. Radiographic measurements of the misalignment angle will be retrospectively recorded and analyzed.

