2.2 Secondary Endpoints

- Length of stay
 - Aim: Decrease length of hospital stay
 - Measured: Time (Hours)
- Length of time for initial image processing
 - Aim: Decrease disturbance to surgeon workflow
 - Measured: Time (Minutes)
- Length of time to place all screws
 - Aim: Reduce the time for screw placement
 - Measured: Time (Minutes)
- Length of time to confirm screw placement
 - Aim: Reduce the time needed for confirmation of screw location
 - Measured: Time (Minutes)
- Length of time to register images
 - Aim: To reduce time for registration of reference images
 - Measured: Time (Seconds)
- Estimated Blood Loss (EBL)
 - Aim: To reduce the EBL of each case
 - Measured: Milliliters (mL)
- Incidence of Malalignment
 - Aim: To decrease the incidence of pedicle screw malalignment
 - Measured: Misalignment angle between pilot hole and screw trajectory (degrees)
- Complications: Neurological Deficits, Dural Tears, deep wound infections, etc
 - Aim: To decrease the incidence of intraoperative complications
 - Measured: number of reported complications while hospitalized
- Measurement of 2D fluoroscopy radiation exposure
 - Aim: to reduce patient and surgeon exposure to radiation
 - Measured: Exposure measured by Dose Area Product (DAP)

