4. STATISTICS

4.1 Sample Size Analysis

- **Student's t-test, ANOVA, chi-square, regression, etc.:** Independent samples T-test
- **Alpha level:** 0.05
- **Beta or power level:** 0.883
- **Primary outcome variable estimate (mean +/- s.d. for continuous outcome, frequency/ percentage for categorical variable):** Total length of operative time (minutes) as determined by the official recorded operative notes
- **Number of groups being compared (use 1 for paired analysis within the same subjects):** 2
- **Effect size or change expected between groups:** Estimated change difference in length of operative time of five (5) minutes with equivalence margins of 40 minutes
- **Resulting number per group:** 65 per group; 130 patients total

A priori power analysis is based on recorded estimates of operative time for 1, 2, and 3-level fusion surgeries. Average length of surgery for 1, 2, and 3-level fusion surgeries are 230, 275, and 325 minutes, respectively. Estimated pooled standard deviation was set at 70 minutes, representing 22 to 30% of the mean operation time for the single and multi-level surgeries. In a non-inferiority model using an independent sample t-test, group sample sizes of 65 patients in two study groups achieves 88% power (with statistical significance defined as alpha equal to 0.05) to detect non-inferiority where the margin of equivalence is 40 minutes and the true difference between study groups is estimated to be 5 minutes.

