4.2 Data Analysis

Data analysis of the study will include:

Descriptive statistics will report means and standard deviations for continuous variables of the study population. Frequencies and percentages will be used to report all discrete variables. Tests of normality for continuous variables will be evaluated using Shapiro-Wilks tests. For those that are non-parametric, Mann-Whitney U tests will be used.

Analysis of the primary outcome will use independent samples t-tests to compare the mean length of surgery between the two study arms.

Comparison of secondary outcomes between patients who undergo posterior spine fusion surgery using 2D fluoroscopy versus those who undergo the same procedure under 3D MvIGS intraoperative navigation guidance will use independent samples t-tests to analyze length of hospital stay; time for initial image processing; time to place all pedicle screws; time to confirm screw placement; time to register images; estimated blood loss; and amount of radiation exposure. Chi-square (or Fisher's exact) tests will be used to compare differences in incidence of malalignment and rate of complications between the two study groups.

To adjust for any potential confounding, multivariable regression models will be generated to report the adjusted effect of which spine navigation technique is used on length of surgical time.

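### Section 3.3 does not keep the reader of the misalignment angle from knowing the arm, and no cut-off in degrees defines a malaligned screw

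*Combined protocol and SAP*

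**What the plan says.** Section 3.1 describes the design: "This is a single center, non-randomized, prospective cohort study to comparatively evaluate the implementation of the MvIGS spine navigation system to conventional 2D fluoroscopy". The synopsis separates the arms by guidance technique, 3D navigation in one and 2D fluoroscopy in the other, so the operating team knows the arm.

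Section 2.2 lists malalignment among nine secondary endpoints, with a direction attached: "Aim: To decrease the incidence of pedicle screw malalignment". The measurement is an angle, in degrees, between the pilot hole and the path of the screw.

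Section 3.3 is the only text on how that angle is obtained: "Radiographic measurements of the misalignment angle will be retrospectively recorded and analyzed". It does not say who reads the films, how many readers there are, which images are used, in what order they are read, or whether the reader knows the arm. Masking is not mentioned anywhere in the document.

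Section 4.2 analyses the endpoint as a proportion: "Chi-square (or Fisher's exact) tests will be used to compare differences in incidence of malalignment and rate of complications between the two study groups". It gives no cut-off in degrees and does not say whether the unit is the screw or the patient.

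**The concern.** A radiographic angle depends partly on the reader's judgement of where lines are drawn. If the reader knows the arm and the stated hope is fewer malaligned screws with the device, borderline films can be read in one direction. The missing cut-off adds to this: the angle must be turned into a yes or no before the test in section 4.2 can be run, and as written that threshold could be chosen after the angles are known.

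The endpoint matters to the study's message. Section 1.5 puts accurate screw placement at the centre of the rationale and projects that operative time will be similar in the two arms. Accuracy is therefore one of the places where a benefit might be claimed. Section 3.2 says the data will be used to evaluate the system's efficacy, and section 9 foresees reports to regulatory authorities.

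The planned analysis would not repair the problem. The multivariable regression in section 4.2 addresses surgical time only, and adjusting for patient characteristics does not remove measurement error that is tied to the arm.

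**Working it through.** **1. The plan's own figure.** The only design calculation is in section 4.1 and concerns operative time. Its inputs are "Alpha level: 0.05", "Beta or power level: 0.883", an SD of 70 minutes, 65 per group, and "Estimated change difference in length of operative time of five (5) minutes with equivalence margins of 40 minutes".

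- Distance to the margin: 40 − 5 = 35 minutes.
- Standard error: 70 × √(2/65) = 12.28 minutes.
- Noncentrality: 35 / 12.28 = 2.85.
- Noncentral t with 128 degrees of freedom, one-sided 0.05: power 0.883, as stated.

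Nothing in this calculation involves the misalignment angle, so changing how films are read leaves both 65 per group and 0.883 as they are.

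**2. What reading bias could do, per patient.** The document gives no malalignment rate, no SD for the angle and no reader error. The following are assumptions:

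- n = 65 patients per arm (section 4.1), each classed as malaligned or not.
- True rate 15% in both arms, so any significant result is false.
- Reading alone opens a gap b between arms, split evenly: read rates of 15% + b/2 and 15% − b/2.
- Two-sided 0.05 chi-square without continuity correction.

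The test statistic is z = (x₁ − x₂)/65 ÷ √[p̄(1 − p̄) × 2/65], where p̄ is the pooled read rate. The chance of |z| > 1.96 was summed exactly over the two binomial distributions. For a hand check, the standard error is √(0.15 × 0.85 × 2/65) = 0.0626, and the chance is about Φ(b/0.0626 − 1.96) + Φ(−b/0.0626 − 1.96).

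| Gap from reading (points) | Read rates | b / 0.0626 | Hand check | Exact sum |
|---|---|---|---|---|
| 0 | 15% v 15% | 0 | 5% | 4.8% |
| 5 | 17.5% v 12.5% | 0.80 | 13% | 12% |
| 10 | 20% v 10% | 1.60 | 36% | 35% |
| 15 | 22.5% v 7.5% | 2.40 | 67% | 68% |

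**3. The same question per screw.** Bilateral screws at one to three levels give 4 to 8 screws per patient. At an assumed average of 6, that is 65 × 6 = 390 per arm. Suppose both true rates are 15% and reading lowers one arm to 10%:

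- Pooled rate 0.125; standard error √(0.125 × 0.875 × 2/390) = 0.0237; z = 0.05/0.0237 = 2.11; p = 0.035. This treats screws in the same patient as independent.
- With an assumed intraclass correlation of 0.05, the design effect is 1 + 5 × 0.05 = 1.25, z = 2.11/√1.25 = 1.89, p = 0.059.
- With 0.10, the design effect is 1.5, z = 2.11/√1.5 = 1.72, p = 0.085.
- Per patient at 65 per arm, the standard error is √(0.125 × 0.875 × 2/65) = 0.058, z = 0.86, p = 0.39.

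The per-screw figure depends heavily on independence and on a unit of analysis that section 4.2 does not state. The per-patient table is the safer illustration.

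**The case against.** The strongest reply is that the plan is silent on masking and does not rule it out. A reader might infer from the design that films will be read openly, or that the study is declared open-label. The document says neither. What stands is that masking is not specified; whether it would be done in practice cannot be known from the text.

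A reader might also infer that the cure is free, because a reader already in place could simply be handed masked films. The document names no reader and describes no staffing, and someone would have to prepare the films. What stands is that masking needs no additional reader, since somebody must read the films in any case, but it does take preparation time.

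Feasibility is a fair challenge. The angle needs the direction of the pilot hole as well as that of the screw, and the plan does not say which images show the pilot hole. If they come from navigation output in one arm and fluoroscopy in the other, the type of image could reveal the arm after all labels are removed. This limits how complete the masking can be, and it is also a reason to name the image source.

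Finally, this is one secondary endpoint of nine. The primary endpoint is operative time from the official operative notes, which the film reader does not affect. That is correct and keeps the point modest.

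**Conclusion.** The point holds as a gap in specification with an inexpensive remedy. The plan combines a reader-dependent angle, a known direction of interest, arms that the operating team can tell apart, no protection of the reader from knowledge of the arm, and no threshold for malalignment. Together these allow bias toward the device on this endpoint.

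The documents do not show that such bias will occur, nor how large it would be. The rise from about 5% to about 12%, 35% or 68% rests on an assumed 15% true rate, one yes-or-no result per patient, and assumed gaps of 5, 10 or 15 points. A reader might take the per-screw p of 0.035 as evidence that a modest shift is enough for a false finding. It is significant only if screws within a patient are nearly independent: it becomes 0.059 at an intraclass correlation of 0.05, and 0.39 per patient.

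This is a desirable improvement to a secondary endpoint. It does not threaten the primary comparison or the sample size.

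**What to change.** Add to section 3.3:

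- the role of whoever reads the films, and the images used for both the pilot hole and the screw, with the same image type in both arms where possible;
- films stripped of arm, date and surgeon, and presented in random order;
- a record of any images that reveal the arm despite this;
- the cut-off in degrees that defines malalignment, set before reading begins and repeated in section 4.2 beside the chi-square test;
- readings locked before arm labels are merged.

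Cost: some coordinator time to de-identify and shuffle about 130 film sets. No extra reader or extra imaging is needed, because the reading is already planned to take place after surgery. Masking may remain incomplete if the pilot-hole images differ by arm, and the report should then say so. Enrolment, operative time, 65 per group and the stated power do not change.

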3.4 Clinical Visits: Scheduling and Requirements

No clinical visits will be required for patients enrolled in this study following discharge of index admission.

3.5 Selection of Patients

3.5.1 Criteria for Inclusion

Patients are included in the study if all of the following criteria are met:

- 1) Diagnosis of spinal stenosis of the lumbar spine with \leq grade 2 degenerative spondylolisthesis
- 2) Skeletally mature adults between the ages of 18-85 years at the time of surgery;
- 3) Has completed at least 6 months of conservative therapy;
- 4) Personally signed and dated informed consent document prior to any study-related procedures indicating that the patient has been informed of all pertinent aspects of the study.

3.5.2 Criteria for Exclusion

Patients are excluded from participating in this study if any of the following criteria are met:

- 1) Gross instability, defined as > 3 mm translational motion on flexion/extension studies;
- 2) Degenerative spondylolisthesis $>$ grade 2
- 3) Degenerative scoliosis $> 10^\circ$ at any level in lumbar spine;
- 4) Congenital lumbar spinal stenosis;
- 5) Endplate changes;

- 6) Visible change in disc height;
- 7) Radiographic confirmation of facet joint disease or degeneration;
- 8) Prior surgery at any lumbar level including the level being treated except for: Lamino/Foraminotomy, Microdiscectomy, IDET, and Percutaneous Discectomy;
- 9) Any evidence of a prior/current fracture, compromised vertebra, current or past trauma, or tumor at affected level or the spinous processes at the adjacent levels;
- 10) Requires destabilizing surgical decompression that adversely affects the functioning of the facets;
- 11) Cauda equina syndrome defined as neural compression causing neurogenic bowel (rectal incontinence) or bladder dysfunction (bladder retention or incontinence);
- 12) Significant peripheral neuropathy or acute denervation secondary to radiculopathy, caused by conditions other than spinal stenosis;
- 13) Significant peripheral vascular disease (diminished dorsalis pedis or tibial pulses);
- 14) Morbid obesity, defined as BMI $> 40 \text{ kg/m}^2$;
- 15) Active systemic or local infection;
- 16) Active Hepatitis (receiving medical treatment within two years);
- 17) Immunocompromised such as but not limited to Acquired Immunodeficiency Syndrome (AIDS), HIV infection, Severe Combined Immunodeficiency Syndrome, Thymic Hypoplasia;
- 18) Insulin dependent diabetes mellitus or any other medical condition(s) that would represent a significant increase in surgical risk or interfere with normal healing;
- 19) Immunologically suppressed, or has received systemic steroids, excluding nasal steroids, at any dose daily for > 1 month within last 12 months;
- 20) History of Paget's disease, osteomalacia, or any other metabolic bone disease;
- 21) Active malignancy. A patient with a history of any invasive malignancy (except non-melanoma skin cancer), unless treated with curative intent and there has been no clinical signs or symptoms of the malignancy > 5 years;
- 22) Involved in study of another investigational product that may affect outcome;
- 23) Women who are pregnant, lactating or anticipate becoming pregnant within 24 months post-surgery;
- 24) Patients who are incarcerated;
- 25) Worker's compensation cases;
- 26) Patients involved in active litigation relating to his/her spinal condition;

3.6 Description of MvIGS Spine Navigation System

3.6.1 Materials

The equipment includes:

1. Proprietary imaging software
2. Integrated surgical light with embedded tracking technology
3. Cart with Arm and Head attachments
4. Surgical Instruments: reference clamp, awl tip, and pedicle probe

3.6.2 Intended Use of the Device

The MvIGS spine navigation system is intended for spatial positioning and orientation of surgical instruments during pedicle screw implantation in patients undergoing posterior fixation in single or multiple levels. The surgical light is intended to be the sole luminaire during image guided surgery.

3.6.3 Indication for Use under Study

The MvIGS spine navigation system is a stereotaxic image guidance system indicated for use in posterior approach spine surgery where reference to a rigid anatomical structure can be identified.

3.7 Investigator Training

The utilization of the MvIGS spine navigation system should be performed only by experienced spinal surgeons with specific training. Implantation of pedicle screw spinal systems is a technically demanding procedure presenting a risk of serious injury to the patient. All warnings, precautions, and recommendations must be fully understood by the operating surgeon prior to surgery. Investigators will use a posterior surgical approach. The use of the intraoperative spine navigation does not alter the surgical technique so much as it is a tool in which the surgeon can utilize to further refine their surgical technique.

3.8 Study Procedures

3.8.1 Enrollment/Preoperative Visit

Patients who meet all the inclusion criteria and who do not meet any of the exclusion criteria specified on the eligibility form will be asked to enroll in the study. Information on screening failures will be collected in a screening log. Patients agreeing to participate in this study must then sign the informed consent.

3.8.2 Post-Operative Visits

Patients will be clinically followed throughout the course of their hospital admission. No visits following discharge will be required.

3.8.3 Patient Disposition

Patients will either complete all the necessary study requirements or their participation in the study may end prematurely for one or more reasons.

Patients will be termed “**discontinued**” from the study for the following reasons:

- **Patient voluntarily withdraws from the study:** A patient may voluntarily withdraw from the study at any time.

3.8.4 Withdrawal Documentation

The reason for patient withdrawal must be fully documented. Study numbers assigned to patients who do not complete the study or discontinue will not be reassigned to newly enrolled patients. Patients who have discontinued should be requested to maintain contact and continue to have assessments whenever possible.

4. STATISTICS

4.1 Sample Size Analysis

- **Student's t-test, ANOVA, chi-square, regression, etc.:** Independent samples T-test
- **Alpha level:** 0.05
- **Beta or power level:** 0.883
- **Primary outcome variable estimate (mean +/- s.d. for continuous outcome, frequency/ percentage for categorical variable):** Total length of operative time (minutes) as determined by the official recorded operative notes
- **Number of groups being compared (use 1 for paired analysis within the same subjects):** 2
- **Effect size or change expected between groups:** Estimated change difference in length of operative time of five (5) minutes with equivalence margins of 40 minutes
- **Resulting number per group:** 65 per group; 130 patients total

A priori power analysis is based on recorded estimates of operative time for 1, 2, and 3-level fusion surgeries. Average length of surgery for 1, 2, and 3-level fusion surgeries are 230, 275, and 325 minutes, respectively. Estimated pooled standard deviation was set at 70 minutes, representing 22 to 30% of the mean operation time for the single and multi-level surgeries. In a non-inferiority model using an independent sample t-test, group sample sizes of 65 patients in two study groups achieves 88% power (with statistical significance defined as alpha equal to 0.05) to detect non-inferiority where the margin of equivalence is 40 minutes and the true difference between study groups is estimated to be 5 minutes.

4.2 Data Analysis

Data analysis of the study will include:

Descriptive statistics will report means and standard deviations for continuous variables of the study population. Frequencies and percentages will be used to report all discrete variables. Tests of normality for continuous variables will be evaluated using Shapiro-Wilks tests. For those that are non-parametric, Mann-Whitney U tests will be used.

Analysis of the primary outcome will use independent samples t-tests to compare the mean length of surgery between the two study arms.

Comparison of secondary outcomes between patients who undergo posterior spine fusion surgery using 2D fluoroscopy versus those who undergo the same procedure under 3D MvIGS intraoperative navigation guidance will use independent samples t-tests to analyze length of hospital stay; time for initial image processing; time to place all pedicle screws; time to confirm screw placement; time to register images; estimated blood loss; and amount of radiation exposure. Chi-square (or Fisher's exact) tests will be used to compare differences in incidence of malalignment and rate of complications between the two study groups.

To adjust for any potential confounding, multivariable regression models will be generated to report the adjusted effect of which spine navigation technique is used on length of surgical time.

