ionizing radiation exposure. In addition to sparing the patient and surgeon to radiation exposure, this new spine navigation system, named the Machine-vision Image Guided Surgery (MvIGS) system, is also projected to not increase mean operative. By use of Instant Flash™ registration, localizing reference images are generated in a matter of seconds, as opposed to minutes, and thereby mitigate the disturbance to normal surgeon-defined workflow.

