1.5 Clinical Study Rationale

Posterior fixation is the standard of care for spinal instability and deformity. Of paramount importance are the accurate placement of transpedicular screws and the avoidance of adjacent neurovascular structures. Intraoperative 3D navigation systems are becoming increasingly popular yet conventional 2D fluoroscopy remains the more widely used modality (Hartl). Worldwide consensus from 677 spine surgeons reported the need for more data regarding surgical precision, operative time and radiation exposure, among other factors, for computer-assisted surgery (CAS) to become more widely accepted.

The purpose of this study is to evaluate the use of the MvIGS spine navigation system for pedicle screw fixation guidance and its effect on the length of operation. It is projected that the length of operation will remain similar to cases where conventional 2D fluoroscopy is utilized.

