2 CLINICAL ASSESSMENTS

2.1 Primary Endpoint

The primary endpoint is based on the mean reduction in total length of operative time. Operative time will be determined by the official recorded operative notes.

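### The trial is powered for non-inferiority with a 40-minute margin, but the analysis section gives the primary test no margin or success rule and the endpoint is worded as a reduction

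*Combined protocol and SAP*

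**What the plan says.** Section 4.1 (Sample Size Analysis) describes an independent-samples t-test in a non-inferiority framework with alpha 0.05, a pooled SD of 70 minutes and 65 patients per group. It claims 88% power "to detect non-inferiority where the margin of equivalence is 40 minutes and the true difference between study groups is estimated to be 5 minutes". The itemised list in the same section uses equivalence terms: "Estimated change difference in length of operative time of five (5) minutes with equivalence margins of 40 minutes". It states neither whether alpha is one- or two-sided nor which arm the 5 minutes favours.

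Section 4.2 (Data Analysis) gives the primary analysis in one sentence: "Analysis of the primary outcome will use independent samples t-tests to compare the mean length of surgery between the two study arms". The continuous secondary outcomes, for which no margin exists, get the same test. Section 4.2 also has a general rule after normality testing, "For those that are non-parametric, Mann-Whitney U tests will be used", and plans that "multivariable regression models will be generated to report the adjusted effect of which spine navigation technique is used on length of surgical time". None of these sentences mentions a margin.

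Section 2.1 and the synopsis define the endpoint this way: "The primary endpoint is based on the mean reduction in total length of operative time". The background expects something else. Section 1.2 says the system "is also projected to not increase mean operative" time, and section 1.5 says: "It is projected that the length of operation will remain similar to cases where conventional 2D fluoroscopy is utilized".

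**The concern.** The hypothesis that justifies 130 patients appears only in the sample size section. The 40-minute margin and the terms non-inferiority and equivalence occur nowhere else in the document. An analyst who follows section 4.2 together with the endpoint definition would test for zero difference and look for a reduction. An analyst who follows section 4.1 would test against +40 minutes. These are different questions, and the same data can answer them differently.

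Two other parts of section 4.2 leave the rule open. The Mann-Whitney sentence does not exempt operative time and, as specified, tests no margin. The study is non-randomised (section 3.1), and an adjusted estimate of the same effect is planned without saying whether it or the t-test decides.

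At stake is the trial's single primary conclusion. If the reduction reading is used, the trial is very unlikely to succeed. If a non-significant difference were reported as similarity, the error rate at the margin would not be held at 5%. No passage says this will be done, but no passage rules it out.

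**Working it through.** **Inputs (all from section 4.1).** n = 65 per group, SD = 70 min, margin = 40 min, true difference = 5 min, alpha = 0.05. Differences are MvIGS minus 2D fluoroscopy, so positive means MvIGS takes longer.

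**Common quantities.** SE = 70 × √(2/65) = 12.28 min; df = 2 × 65 − 2 = 128. Critical values are t(0.95) = 1.657 and t(0.975) = 1.979.

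**Step 1: reproduce the plan's power.** Power = P(noncentral t, 128 df, ncp = (40 − δ)/12.28, exceeds the critical value).

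| Reading of section 4.1 | Power |
|---|---|
| Non-inferiority, one-sided 0.05, δ = +5 (ncp = 35/12.28 = 2.85) | 0.8831 |
| Non-inferiority, one-sided 0.05, δ = −5 (ncp = 45/12.28 = 3.66) | 0.9773 |
| Non-inferiority, one-sided 0.025, δ = +5 | 0.8076 |
| Equivalence, two one-sided tests at 0.05, margins ±40, δ = +5 | 0.8603 |

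The stated 0.883 is reproduced. Of these readings, only one-sided 0.05 with the 5 minutes toward the margin gives it. The equivalence figure was obtained by integrating over the sampling distribution of the variance.

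**Step 2: run section 4.2 as a test for a reduction.** With a two-sided 0.05 test of zero difference, P(significant reduction) = P(noncentral t with ncp = δ/12.28 is below −1.979).

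- δ = +5 (ncp 0.41): 0.9%.
- δ = −5 (ncp −0.41): 6.0%.

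**Step 3: compare the decision limits at an observed SD of 70.**

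- Largest observed excess that passes the margin: 40 − 1.657 × 12.28 = 19.7 min.
- Smallest significant difference from zero: 1.979 × 12.28 = 24.3 min.

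An observed excess between 19.7 and 24.3 min is non-significant and also fails non-inferiority. Allowing the sample SD to vary, the probability of being both non-significant and failing the margin is 5.8% at δ = +5, 14.6% at δ = +20 and 5.2% at δ = +40.

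**Step 4: error at the margin if non-significance were read as similarity (illustrative).** P(two-sided zero-difference test is non-significant) when δ = +40:

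| SD (min) | Error at true +40 |
|---|---|
| 60 | 3.5% |
| 70 | 10.1% |
| 80 | 19.2% |

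This equals 5% at SD 62.8. The non-inferiority test holds the error at 5% whatever the SD.

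**The case against.** Section 4.1 is more than a bare sample size line. It names the test, the alpha, the margin and a non-inferiority framework, and section 4.2 names the same test for the same outcome. Sections 1.2 and 1.5 fit that reading. The stated power points to one-sided 0.05 non-inferiority rather than equivalence, so the equivalence terms may be loose wording. The 10.1% error assumes a practice the plan does not describe, and the 19.7 to 24.3 minute band holds only at an observed SD of 70. The Mann-Whitney sentence sits in a general paragraph, and the specific t-test sentence that follows may override it. The choice between adjusted and unadjusted estimates is a separate question that would exist even with a margin in place.

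Much of this is fair. A rule can be partly inferred from section 4.1, and non-inferiority is probably what was meant. The Step 4 figures are illustrative, and the Mann-Whitney and adjusted-estimate points are secondary. The central gap remains. Sidedness and direction can be recovered only by back-calculating the power, section 4.2 states no decision rule, and the endpoint definition in two places points to a different hypothesis. A primary success criterion should not depend on that inference.

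**Conclusion.** The concern holds and should be fixed before analysis. The sample size arithmetic is sound; the fault is that the powered hypothesis does not reach the analysis section or the endpoint definition. Under the plan's own inputs (SD 70, 65 per arm, true difference 5 minutes), the intended test has 88.3% power. The reduction reading has a 0.9% or 6.0% chance of success, depending on which arm the 5 minutes favours.

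The power figures assume equal SDs, approximately normal means and the unadjusted comparison. Reading non-significance as similarity would put the error at the margin above 5% only if the SD exceeds 62.8 minutes, which the planned 70 does.

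**What to change.** **Essential changes**

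- In section 4.2, state the rule: MvIGS is non-inferior if the upper limit of the two-sided 90% CI (one-sided alpha 0.05) for mean operative time, MvIGS minus 2D fluoroscopy, is below +40 minutes.
- In section 2.1 and the synopsis, reword the endpoint as the difference in mean operative time.
- In section 4.1, state the sidedness and the direction of the 5 minutes, and use the term non-inferiority margin throughout. If equivalence is intended, restate the power as about 86%.
- State that a non-significant test of zero difference will not be reported as similarity.

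**Supporting changes**

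- State that a Mann-Whitney test of zero difference will not replace the margin-based analysis. If a rank method is wanted for skewed times, define it against the same margin.
- Report the adjusted regression estimate with its CI against the same margin, with number of levels fused among the covariates, and say in advance which estimate decides.

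**Cost.** Wording only: no extra patients or data, and 130 stays. Power remains 88.3% for the unadjusted 90% CI rule and becomes about 81% if a 95% CI is chosen. If the adjusted estimate decides, its power depends on residual variance and covariate imbalance. The documents give neither, so it cannot be computed here, and the protocol should note that 88.3% applies to the unadjusted t-test.
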